4.4 Randomization Procedures and Blinding

Randomization Procedures

All subjects will receive open-label C1-INH during Treatment Period 1. Subjects who are eligible for Treatment Period 2 will be assigned to either continued C1-INH or matched placebo in accordance with a computer-generated randomization list. Investigational product assigned in Treatment Period 2 will be allocated on a 1:1 ratio. The randomization will be stratified on the following 2 factors:

- Donor Specific Antibodies (DSA): sensitized prior to transplantation versus de novo. De novo is defined as the development of DSA after transplantation. In the case of both sensitized and de novo, the subject will be considered sensitized for stratification purposes.
- AMR severity: severe versus non-severe (ie all other severities). Severe AMR is defined as new onset oliguria (< 400 cc / 24 hours) or anuria with the current episode of AMR.

Therefore, there will be a total of 4 strata (2 factors, 2 levels per factor). The randomization will be permuted block within each stratum. Treatment assignment will be determined centrally. The randomization list will be generated and managed by the study's interactive response technology (IRT) external service provider.

The study database will be locked once all the randomized subjects currently in the study complete week 38 visit and re-treatment period as described in [Section 3](#). The study will be unblinded for final analysis of the primary efficacy endpoint.

Maintaining the Blind

Treatment Period 1 is open-label. Treatment Period 2 is double-blind. During Treatment Period 2, the blind will be maintained for investigational site staff, including investigators, subjects, and CSL.

Emergency Unblinding

In emergency situations involving the safety of the subject, the investigator may break the blind using the IRT system. The reason for unblinding the randomization code must be fully documented. Emergency unblinding will be performed using the IRT. Steps for navigating the IRT for emergency unblinding are defined in the IRT manual.

4.5 Determination of the Sample Size

Sample Size Based on the Primary Efficacy Endpoint

The sample size is based on the primary efficacy endpoint of loss-of-response status (binary endpoint of loss-of-response or not), at the End-of-TP2 (ie, within 25 weeks after randomization). The null hypothesis is that there is no difference between C1-INH and placebo with respect to the proportion of subjects with loss-of-response at the End-of-TP2. Let p_0 and p_1 be the expected proportion of subjects with loss-of-response in TP2 in the placebo and C1-INH treatment groups, respectively. The alternative is that there is a difference between the treatment groups. That is, $H_0: p_0 = p_1$ versus $H_1: p_0 \neq p_1$.

[figure not shown]
The power procedure in SAS STAT software (Cary, NC SAS Institute Inc.) was used to estimate the sample size, based on the likelihood ratio chi-square test. Determination of the sample size was based on the following assumptions:

- The proportions of subjects experiencing loss-of-response at the End-of-TP2 will be 0.75 with placebo and 0.30 with C1-INH.
- There will be at least 90% power to detect a statistically significant effect with two-sided test with alpha = 0.05.
- Logistic regression model with treatment effect will be used for the primary efficacy analysis. Wald test statistic for treatment effect from Logistic regression has approximately same distribution as chi-square [Fleiss et al, 2003]. Therefore, the sample size calculation based on chi-square test is used to ensure similar power for hypothesis testing.
- Treatment allocation will be 1:1.

- The planned interim analysis for futility will not impact the type 1 error for the final analysis. Under these assumptions, a total of 60 subjects (30 randomized to C1-INH and 30 randomized to placebo) will provide approximately 95% power. The study was planned to enroll a sufficient number of subjects (up to 175) to ensure that 60 subjects are randomized.

The assumptions above are based on a prospective single-arm pilot study to investigate the C1- INH added to high-dose IVIG for the treatment of acute AMR non-responsive to conventional therapy [Viglietti et al, 2016a]. A total of 6 subjects received C1-INH and IVIg for 6 months. The primary endpoint was change in eGFR. These were compared to a historical control of 21 subjects who received IVIg. In the prospectively treated C1-INH group, 0/6 subjects experienced decline in eGFR at 6 months (0; 95% confidence interval [CI], 0 to 46%); and 4/6 subjects had a greater than 20% increase in eGFR (67%; 95% CI, 22% to 96%). In the historical control group, 15/21 subjects (71%; 95% CI, 48% to 89%) experienced decline in eGFR during a comparable 6-month period. The results are presented in Figure 2.

Figure 2 Individual variations of eGFR in C1-INH patients

Left: Distributions of eGFR at time of initial diagnosis (M-3), at the end of first line treatment (SOC; M0) and at the end of C1-INH treatment (M+6) in 6 patients. Right: Individual variations in eGFR between M0 and M+6 in C1-INH patients (green) and historical controls (red). From Viglietti et al. (Viglietti et al, 2016b)

Power for the analysis of all-cause allograft failure

Allograft survival status (or all-cause allograft failure) at the end of 48 months after enrollment represents clinical confirmation of the effect on the allograft of improving eGFR.

The primary comparison of the proportion of subjects with allograft survival will be between the subjects randomized to placebo or C1-INH. It is anticipated that very few subjects will be lost to follow-up as standard of care mandates close follow up by the transplanting center. This endpoint will be analyzed after all subjects have been followed for 4 years after enrollment.

[figure not shown]
The power for hypothesis testing of this endpoint was estimated using the power procedure in SAS STAT under the following assumptions:

- The proportions of subjects with allografts surviving at 4 years after enrollment will be 0.25 with the placebo cohort and 0.75 in the C1-INH cohort.
- Alpha = 0.05 (two-sided test).
- Logistic regression model with treatment effect will be used for the primary efficacy analysis. Wald test statistic for treatment effect from Logistic regression has approximately same distribution as chi-square [[Fleiss et al, 2003](#)]. Therefore, the sample size calculation based on chi-square test is used to ensure similar power for hypothesis testing.
- Approximately 30 subjects in each randomized treatment groups.

There is greater than 90% power to detect the specified target difference between C1-INH and placebo groups based on sample size of 60 (approximately 30 in the C1-INH cohort and approximately 30 in the placebo cohort).

The 4-year graft survival for placebo of 25% is based on data presented at the American Transplant Congress in Boston [[Viglietti et al, 2016b](#)], as shown in [Figure 3](#). This study involved follow-up of kidney transplant recipients with biopsy-proven active AMR diagnosed between 2007 and 2013. Among the subjects who have not responded to standard of care, the 4-year graft survival ranged from approximately 10% to 40% for subjects with high and intermediate risk scores, respectively. The 4-year graft survival for C1-INH of 75% represents what would be expected for subjects who are successfully treated.

Figure 3 Stratification of Graft Survival After ABMR Therapy Based on Prognostic Scoring

Source: [Viglietti et al, 2016b](#) American Transplant Congress Abstract #198

4.6 Planned Interim Analyses and Reviews

The study will be monitored by an Independent Data Monitoring Committee (IDMC). The meeting frequency, specific responsibilities, and composition of the IDMC will be outlined in a separate document, the IDMC charter.

The study was terminated by the sponsor on 15 September 2020, therefore, no interim analysis will be conducted.

5 Changes in the Conduct of Planned Analyses

There are changes in the planned analyses (from those specified in the protocol) following the sponsor's decision to terminate the study. There will be no analysis of the endpoints below. Data from these endpoints will be presented only in subject listings.:.

- Secondary endpoint of proportion of subjects with all-cause allograft failure through the Responder Follow-up Period,
- Time to all-cause allograft failure through 48 months after enrollment,
- Change in eGFR from End-of-TP1 to the End-of-TP2,
- Rate of change of eGFR in Treatment Period 2,
- CCI [REDACTED],
- Plasmapheresis sessions,
- CCI [REDACTED]
[REDACTED],
- CCI [REDACTED]
[REDACTED],
- CCI [REDACTED]
[REDACTED],
- Trough IVIg concentrations at designated time points,
- CCI [REDACTED],

For other endpoints the statistical analysis was reduced as described in the sections of this SAP.

6 Study Analysis Sets

6.1 Screened Analysis Set

The Screened analysis will comprise all subjects who provided written informed consent and who underwent study screening procedures.

6.2 Enrolled Analysis Set

The Enrolled Analysis Set will comprise all subjects in the Screened Analysis Set who did not fail screening.

6.3 Intent-to-Treat Analysis Set

The Intent-to-Treat (ITT) analysis will comprise all subjects who were randomized. Subjects will be classified according to the investigational product to which they were assigned (ie, continued C1-INH or placebo) regardless of what was actually received. This will be the primary analysis

set for the analysis of efficacy data. Any subject who received a randomization identification number will be considered to have been randomized.

6.4 Modified Intent-to-Treat Analysis Set

All subjects randomized under the original protocol and under all protocol amendments will be included in the Modified ITT (mITT) population except the subjects randomized prior to Amendment 3 who did not satisfy the eligibility criteria updated in Amendment 3. The mITT Analysis Set will be the primary analysis set for the analysis of efficacy data.

6.5 Safety Analysis Sets

Run-in Safety Analysis Set

The Run-in Safety (RiS) Analysis Set will comprise all subjects who received at least one dose of C1-INH during Treatment Period 1.

Randomized Withdrawal Safety Analysis Set

The Randomized Withdrawal Safety (RWS) Analysis Set will include all subjects in the ITT Analysis Set who received at least one dose of the investigational product after randomization during Treatment Period 2. The RWS Analysis Set will be based on the investigational product actually received (ie, continued C1-INH or placebo) during Treatment Period 2. If a C1-INH treatment subject receives one or two doses of placebo and then this is corrected for all subsequent doses they will be classified in the C1-INH treatment group.

6.6 Pharmacokinetic Analysis Set

The Pharmacokinetic (PK) Analysis Set will comprise all subjects who received ≥ 1 dose of C1- INH and who have ≥ 1 measurable level of C1-INH functional activity or C1-INH antigen concentration.

6.7 CCI

CCI

7 General Considerations

Analysis datasets will be created according to CDISC standards, and data will be displayed according to reporting standards in this SAP and tables, figures and listings (TFL) formats.

SAS version 9.3 or higher will be used to perform all data analyses and to generate TFLs.

All ICH required data in the database will be presented in data listings.

Continuous variables will be summarized in terms of the number of observations, mean, standard deviation, median, Q1, Q3, minimum and maximum. Other descriptive statistics (eg, quartiles, coefficient of variation) may be reported when appropriate. Categorical variables will be summarized using frequency counts and percentages. Analyses that use other descriptive statistics will have the specific descriptive statistics required identified with the analysis in the applicable SAP section.

All listings will include subject number, treatment group. The laboratory normal reference ranges will be provided and clinical laboratory test results outside the normal reference range will be flagged in the laboratory data listings.

Summary statistics of central tendency will be reported to one more decimal place than the collected data. Summary statistics of variability will be reported to one more decimal place than the commensurate measure of central tendency. For example, the mean and median for age will be reported to one decimal place because it is collected in full years. The standard deviation of age will then be reported to 2 decimal places.

Formatting for dates and times will be: descriptive percentages and proportions will be displayed to one decimal place. Percentages and proportions to be tested will be calculated to 4 decimal places. Durations for events will be display to 1 decimal place.

- Dates only – ddmmmyyyy
- Times only – hh:mm or hh:mm.ss
- Dates and times – ddmmmyyyy hh:mm or ddmmmyyyy hh:mm:ss

In general, only scheduled visits will be included in by-visit summaries. However, worst-case or best-case values (as appropriate) will be derived using both scheduled and unscheduled visits. In general, assessment windows will not be defined for the purpose of classifying measurements obtained outside scheduled assessment times, other than those indicated in the Schedule of Assessments. However, exceptions may apply for creatinine / eGFR.

Actual rather than planned sampling times will be used in the derivation of PK parameters and in the individual concentration-time plots and listing of PK concentration data. Planned times will be used in the descriptive summaries and in mean and median plots. Concentration-time data will be listed according to actual sampling times relative to dosing time.

Deviations from the analyses in this SAP will be identified in the CSR.

7.1 Multicenter Studies

Data from all participating sites will be pooled prior to analysis.

7.2 Treatment Descriptors

The following treatment group descriptor will be used on all applicable displays:

Treatment Group		Order of Treatment Groups
Code	Description	
A	Placebo	1
B	C1-INH	2

7.3 Multiple Comparisons and Multiplicity

No formal hypothesis testing is planned due to small number of subjects randomized in this study when the study was terminated by the sponsor. Hence multiplicity is not applicable.

8 Data Handling Conventions

8.1 Missing Data

Missing data occurs when any requested data is not provided, leading to blank fields on the collection instrument. These data will be indicated by the use of a “blank” in subject listing displays. Answers such as “Not applicable” and “Not evaluable” are not considered to be missing data and should be displayed as such provided in the collection instrument.

8.1.1 Imputation of Non-Date Missing Data

Non-date Clinical Data

All available data will be analyzed using suitable statistical methods. For analysis of percent responders, all subjects in the appropriate analysis set (ITT Analysis Set or mITT Analysis Set) will be included in the denominator when calculating the percentages; any subject who drops out of the study at any time after randomization will be defined for the purpose of analysis as a non-responder.

Subjects with the designation of treatment relationship for adverse events (AEs) and serious adverse events (SAEs) missing will have the worst case assumed to impute the relationship: if relationship to study treatment is missing it will be assumed to be “Yes”.

In summaries of absolute values and change from baseline, subjects with missing baseline values will not be included in baseline rows or in the change from baseline summary statistics.

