10.3.3.1 Primary Efficacy Analysis

The primary analysis of the primary efficacy endpoint of loss-of-response at the End-of-TP2, will be based on a logistic regression model. The randomized treatment groups, C1-INH and placebo, will be compared based on the logistic model.

Subjects will be considered to have lost response if they drop-out or are lost to follow-up before the response status at the End-of-TP2 could be determined.

If π is the probability that an individual in a given treatment group will have a loss-of-response at the End-of-TP2, the logistic model assumes that in each treatment group, binary outcome of response status can be described by a model which assumes independence between subjects. Also, the model assumes that all subjects with the same covariate values have the same probability, such that the logit of π is a linear function of the regression coefficients particular to that individual:

$$\text{Logit}(\pi) = \log(\pi/(1-\pi)) = \alpha + \beta_T X_T,$$

where X_T is the indicator variable for treatment (C1-INH=1, placebo = 0).

Please note the stratification factors for randomization are not included in this model as difference in efficacy is not expected based on these strata. However, subjects have been randomized based on these strata of DSA sensitized versus DSA de novo and AMR severity (severe versus all other severities) to ensure balance among these strata.

The odds ratio for C1-INH versus placebo is $\exp(\beta_T)$ based on this model for primary efficacy analysis. The primary hypothesis to be tested is $H_0: \beta_T = 0$ vs $H_1: \beta_T \neq 0$. This will be tested using the Wald statistic derived from maximum likelihood estimation of the logistic model. If this hypothesis is rejected at the 0.05 level of significance and the point estimate of β_T is positive, efficacy will be declared. The logistic model will be used to provide point estimates of the odds ratio and risk difference, with 95% confidence intervals by treatment groups. Summary statistics of proportion of subjects with loss-of-response will also be presented by treatment. If maximum likelihood estimation of the logistic model fails to converge then exact methods for logistic regression will be used for hypothesis and estimation.

Components of loss-of-response at the End-of-TP2 will be summarized by treatment groups in terms of the proportion of subjects with:

- End-of-TP2 eGFR (mean of Week 36 and Week 38 eGFR values) that is not stable, defined as:

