The mean of Week 36 and Week 38 eGFR measurements. If one of the measurements is missing it is then the non-missing value.

Response to Open-Label C1-INH at End of Treatment Period 1 (End-of-TP1)

Responders are defined as subjects whose End-of-TP1 (the mean of Week 11 and Week 12) eGFR $\geq 90\%$ of baseline and ≥ 20 mL/min/1.73 m². The baseline eGFR is defined as the mean of the screening and Day 1 values in [Section 8.2.5](#).

Loss of Response During Treatment Period 2

Loss-of-response at the End-of-TP2 is defined as any 1 of the following 3 conditions:

- End-of-TP2 eGFR (mean of Week 36 and Week 38 eGFR) that is not stable, defined as:
 - End-of-TP2 eGFR that is $< 90\%$ of the End-of-TP1 eGFR for subjects whose End-of-TP1 eGFR (mean of Week 11 and Week 12 eGFR) is $\geq 100\%$ of baseline;

- End-of-TP2 eGFR that is < 90% of baseline for subjects whose End-of-TP1 eGFR is ≥ 90% of baseline and < 100% of baseline.
- Allograft failure (defined by allograft nephrectomy, or institution of permanent dialysis, or return to the transplant waitlist for renal transplant, whichever occurs first)
- Subject death by any cause.

All-Cause Allograft Failure

All-cause allograft failure within 48 months after enrollment is defined as 1 of the following, whichever occurs first:

- Allograft failure (defined by allograft nephrectomy, or institution of permanent dialysis, or return to the transplant waitlist for renal transplant, whichever occurs first), OR
- Subject death by any cause.

No subject has reached 48 months after enrollment due to study termination.

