10.1 Analysis of Proportion of Subjects With Loss of Response at the End-of-TP2

The number and proportion of subjects with loss of response at the End-of-TP2 will be presented by treatment group along with the confidence interval for the difference between the two groups.

Subjects will be considered to have lost response if they drop-out or are lost to follow-up before the response status at the End-of-TP2 could be determined.

Components of loss-of-response at the End-of-TP2 will be summarized by treatment groups in terms of the proportion of subjects with:

- End-of-TP2 eGFR (mean of Week 36 and Week 38 eGFR values) that is not stable, defined as:
 - End-of-TP2 eGFR that is < 90% of the End-of-TP1 eGFR for subjects whose End-of-TP1 eGFR is \geq 100% of baseline,
 - End-of-TP2 eGFR that is < 90% of baseline for subjects whose End-of-TP1 eGFR is \geq 90% of baseline and < 100% of baseline,
- All-cause allograft failure (ie, allograft nephrectomy, or institution of permanent dialysis, or return to the transplant waitlist for renal transplant),
- Death by any cause.

The primary efficacy analysis will be conducted for the mITT Analysis Set.

10.1.1 Subgroup Analyses of Proportion of Subjects With Loss of Response at the End-of-TP2

The proportion of subjects with loss of response at the End-of-TP2 will be summarized by the treatment group for the following subgroups based on the following subgroup analyses outlined below will be conducted for the mITT Analysis Set.

The following subgroups, and possibly others to be described in the SAP, will be summarized by treatment group with respect to the proportion of loss-of-response:

- Geographic region: USA, non-USA,
- DSA by randomization strata: sensitized, de novo,
- DSA by classification: HLA class I, HLA class II, both HLA class I and II,
- AMR severity: severe, non-severe (all other severities),
- Type of donor: deceased, living,
- Recipient race: Black, non-Black,
- Recipient sex: Male, Female,
- Recipient age: < 65 years, \geq 65 years.

The difference in the proportion of response along with the 95% confidence interval will be also presented for each subgroup.

10.2 Analysis of key Secondary Endpoint Proportion of Subjects With All-Cause Allograft Failure Through the Responder Follow-up Period (ie, Within 48 Months After Enrollment)

No subject will complete the follow-up period of 48 months after enrollment. Therefore, this key secondary analyses cannot be conducted.

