10.5 Analysis of Responders at the End-of-TP1

This analysis will be based on the RiS Analysis Set.

The proportion of responders at the End-of-TP1 will be presented together with an exact 95% confidence interval. Definition of response at End-of-TP1 is given in [Section 8.2.9](#).

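### SAP 8.1.1 turns any drop-out after randomization into a non-responder, while SAP 10.1 and the protocol do so only before End-of-TP2 status is known

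*SAP*

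**What the plan says.** SAP 8.1.1 sets a convention for percent responders in the ITT or mITT set. Everyone in the set stays in the denominator, and "any subject who drops out of the study at any time after randomization will be defined for the purpose of analysis as a non-responder". It gives no end point in time and does not require the status to be missing.

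SAP 10.1, which covers the primary endpoint, counts subjects as having lost response only "if they drop-out or are lost to follow-up before the response status at the End-of-TP2 could be determined". Protocol 10.3.3.1 has the same rule: subjects have "lost response if they drop-out or are lost to follow-up before the response status at the End-of-TP2 could be determined".

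SAP 8.2.9 fixes when that status can be determined. End-of-TP2 eGFR is "The mean of Week 36 and Week 38 eGFR measurements. If one of the measurements is missing it is then the non-missing value", so a single value at either visit is enough.

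SAP section 5, which lists changes from the protocol's analyses, mentions no change to the drop-out rule.

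**The concern.** Two instructions in the same SAP classify the same subject differently, and neither is given precedence. A programmer following 8.1.1 and one following 10.1 would both comply with the plan and could produce different primary tables.

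The period in which they can disagree is long. After End-of-TP2, responders were to be followed for about 39 months. The study was terminated and no subject reaches Month 48. The disposition table in SAP 9.1 also counts discontinuations before Week 208, so many subjects may carry a discontinuation record dated after their primary endpoint was observed. The SAP does not define dropping out, or say whether leaving because the sponsor ended the study counts.

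At stake is the descriptive primary result: the proportion with loss of response by arm, the confidence interval for the difference, and the subgroup tables in SAP 10.1.1.

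**Working it through.** **Does 8.1.1 reach the primary endpoint?** It concerns responders in the ITT or mITT set, counted from randomization. The End-of-TP1 responder analysis is not in those sets; SAP 10.5 says "This analysis will be based on the RiS Analysis Set". The mITT responder outcome that can be read is the TP2 one, and SAP 10.1.1 uses that vocabulary: "The difference in the proportion of response along with the 95% confidence interval will be also presented for each subgroup". On the readable text, 8.1.1 therefore applies to the primary summary and its subgroups. Blacked-out analyses cannot be checked.

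**Where the rules differ.**

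| Randomized subject | SAP 10.1 / Protocol 10.3.3.1 | SAP 8.1.1, literal |
|---|---|---|
| Leaves with no Week 36 or Week 38 eGFR | Loss of response | Non-responder |
| Unstable End-of-TP2 eGFR, graft failure or death by End-of-TP2 | Loss of response | Non-responder |
| Stable End-of-TP2 eGFR, stays | Response | Responder |
| Stable End-of-TP2 eGFR, then leaves | Response | **Non-responder** |

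Only the last row differs. This treats loss to follow-up, which 8.1.1 does not name, as a form of drop-out.

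**The plan's own figure.** The stated power of about 95% (30 per arm, 0.75 versus 0.30, two-sided 0.05) reproduces. With mean proportion 0.525, z = (0.45√30 − 1.96√(2 × 0.525 × 0.475)) / √(0.75 × 0.25 + 0.30 × 0.70) = (2.465 − 1.384) / 0.630, about 1.71, which gives 95.7%. The conflict does not alter that calculation, and no test remains to which it applies.

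**How many subjects.** SAP section 3 gives 13 randomized, with 2 still in treatment at termination. At most 13 − 2 = 11 could already have left by then. How many left after a stable End-of-TP2 result is not stated and may be zero.

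**Effect of one reclassified subject.** The arm's proportion, and the difference between arms, moves by 100/n points. Arm sizes are not given, so the splits are assumptions:

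| Assumed split | Smaller arm | Larger arm |
|---|---|---|
| 6/7 | 1/6 = 16.7 | 1/7 = 14.3 |
| 5/8 | 1/5 = 20.0 | 1/8 = 12.5 |
| 4/9 | 1/4 = 25.0 | 1/9 = 11.1 |

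One subject reclassified in each arm at 6/7 moves the difference by a net 1/6 − 1/7 = 1/42 = 2.4 points.

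**Direction.** Suppose a share q of stable subjects later leaves, equal in both arms (an assumption). At the design rates, the literal rule gives 0.75 + 0.25q on placebo and 0.30 + 0.70q on C1-INH, a difference of 0.45(1 − q): 0.405 at q = 10%, 0.360 at 20%, 0.225 at 50%. If departure through sponsor termination counted as drop-out, q would be 100%, both arms would show 100% loss of response, and the difference would be zero.

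**The case against.** The strongest reply is that context already settles the matter. The clause sits in a section on imputation, under a parent section that explains "Missing data occurs when any requested data is not provided, leading to blank fields on the collection instrument", and its paragraph opens with "All available data will be analyzed using suitable statistical methods". Overwriting an observed result is not imputation. SAP 10.1 is specific to the endpoint and matches the protocol, and a specific rule normally governs a general one. The extreme result under sponsor termination cannot have been intended. All this favours the narrower reading. It does not remove the conflict: the trigger in 8.1.1 is leaving the study, not a blank field, and no sentence gives 10.1 precedence.

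Second, 8.1.1 speaks of responders and 10.1 of loss of response, so the link is inferred, and a blacked-out analysis may be what 8.1.1 serves. That limit stands, but in the readable text the mITT responder outcome is the primary one.

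Third, the figures do not bound the effect. This is fair. The count of 11 is as of termination; the two subjects then in treatment could also enter the disputed group before lock. The primary set is mITT, which may be smaller than 13; at an assumed 3/5 split one subject moves a proportion by 33.3 or 20.0 points. Also, the single-value allowance is in SAP 8.2.9 only. The protocol uses the mean of both visits without a fallback, so it does not settle the case of a subject who leaves between Weeks 36 and 38.

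**Conclusion.** The concern holds. As written, SAP 8.1.1 would replace an observed stable End-of-TP2 outcome with a failure, contrary to SAP 10.1 and Protocol 10.3.3.1.

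It is minor. SAP 4.2.1.3 and 7.3 rule out formal testing, so type I error and decision rules are untouched. The listings of individual eGFR values (SAP 10.6) and of study completion with reasons (SAP 9.1) would let a reader recompute the status. The effect is confined to the descriptive proportions, the interval for the difference and the subgroup tables.

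Confidence is high on the textual conflict. The size of its effect is unknown: zero if nobody left after a stable result, and 11.1 to 25.0 points per reclassified subject over the assumed splits of 13.

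**What to change.** Replace the drop-out clause in SAP 8.1.1 with wording such as:

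> *A randomized subject who leaves the study or is lost to follow-up before End-of-TP2 response status can be determined is counted as loss of response (see Section 10.1). Leaving later, including because the sponsor terminated the study, does not change an End-of-TP2 status already observed.*

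If a blacked-out percent-responder analysis relies on the present general clause, state its drop-out rule in its own section.

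The cost is one sentence in the SAP before database lock and unblinding. It needs no new data and leaves the protocol rule as it is.
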